13.1.2 SECONDARY ENDPOINTS

- Number of patients ventilated with an AnMach in the period of interest (continuous)
- Age (continuous), gender (categorical)

- Reason for admission (categorical)
- APACHE II score (continuous)
- SOFA score (continuous)
- Duration of ventilation - a measurement of the time from the start of ventilation until the first period of mechanical ventilation is complete (continuous)
- Length of ICU stay – A measure of the number of days between admission to ICU and discharge from ICU (continuous)
- Number of days of ventilatory support before weaning ventilation (patients on spontaneous breathing) (continuous)
- Number of days spent weaning from ventilation to being successfully weaned from ventilator (extubation) (continuous)
- Number of days following ventilation with the AnMach after which transfer to an ITU grade ventilator happened (continuous)
- Indication for transferring a patient from an AnMach to the conventional ITU ventilator (categorical)
- Proportion of patients receiving a tracheostomy (frequency)
- Organ support - number of days of (continuous)
 - Use of one or more inotropic drugs or anti arrhythmic
 - Renal - a need for renal replacement therapy
 - Liver - correction of coagulopathy (plasma use), hypoglycaemia (glucose use), presence of hyperlactataemia (high lactate levels) related to liver failure
 - Neuro - delirium
- Length of hospital stay - A measure of the number of days between admission to Hospital and subsequent discharge from hospital (continuous)
- Mortality at 28 days – proportion of patients who died in the study period (frequency)

▪

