 - These will provide more information about the progress of patients while being ventilated. There may be documentation that mentions difficulties that have arisen when ventilating or weaning ventilation in these patients as well as providing indications as to why patients have been switched to different modes of ventilation or device.
 - Physiotherapists' notes may help us to identify the AnMach patients.

3. Data recording and translation to Outcomes/Endpoints

The data for each patient will be recorded and anonymised in an encrypted Excel spread sheet and will include:

- Age, gender
- Reason for admission
- APACHE II score
- SOFA score
- Date of admission to ICU
- Date of intubation
- Was patient ventilated using AnMach?
- Number of days of ventilatory support before weaning ventilation
- Number of days spent weaning from ventilation to being successfully weaned from ventilator (extubation)
- Was patient transferred from AnMach onto conventional ICU ventilator?
- How many days following ventilation with the AnMach did the transfer happen?
- What was the indication for transferring a patient from an AnMach to the conventional ICU ventilator?
- Did the patient receive a tracheostomy?
- Adverse events possibly correlated with the use of AnMach: soda lime issues, gas flow issues, hypoxia, elevate pressure of ventilation, water need to be cleaned out of tubes, sudden respiratory rate increase, need for manual ventilation
- Organ support - number of days of
 - Use of one or more inotropic drugs or anti arrhythmic

- Renal - a need for renal replacement therapy
- Liver - correction of coagulopathy (plasma use), hypoglycaemia (glucose use), presence of hyperlactataemia (high lactate levels) related to liver failure
- Neuro - delirium
- Date of discharge from ICU or date of death
- Length of ITU stay

The above data will be used to identify quantitative values for the primary and secondary endpoints discussed in section 13.1. This will then be analysed as discussed in Section 13.0

9.1.1b - a prospective data collection

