11 DATA MANAGEMENT AND QUALITY ASSURANCE

Data collection points:

- Retrospective data collection: 1st of July – 30th of October 2020
- Survey: 1st of July – 31st of July 2020
- Interviews: 15 July – 31st of Sept 2020

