11.2 DATA COLLECTION TOOL

Data Collection Forms will be designed by the CI and collaborators. All data will be entered legibly in black ink with a ball-point pen. If the Investigator makes an error, it will be crossed through with a single line in such a way to ensure that the original entry can still be read. The correct entry will then be clearly

inserted. The amendment will be initialled and dated by the person making the correction immediately. Overwriting or use of correction fluid will not be permitted.

It is the Investigator's responsibility to ensure the accuracy of all data entered and recorded in the forms. The Staff Delegation of Responsibilities Log RFLRDLOG0004 will identify all trial personnel responsible for data collection, entry, handling and managing the database. The data custodian for this study is [name].

For phase 1, data is to be recorded directly onto the CRF by the CI and the study management team. The data collected is listed in section 9. For phase 2, survey data will be exported in an excel file and kept in a password coded computer. The interview transcriptions will be kept anonymised in word files and saved in a password coded computer for the thematic analysis while the recording destroyed soon after being transcribed.

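### The 28-day mortality endpoint is defined over the study period instead of 28 days, and the listed data items do not supply it or length of hospital stay

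*Protocol*

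**What the plan says.** Section 13.1.2 of the protocol defines one secondary endpoint as "Mortality at 28 days – proportion of patients who died in the study period (frequency"). It gives no starting point for the 28 days and does not define the study period. A second endpoint in the same list is "Length of hospital stay - A measure of the number of days between admission to Hospital and subsequent discharge from hospital (continuous").

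Section 9.1.1a lists the items to be recorded for each patient. The ones that bear on these endpoints are "Date of admission to ICU", the intubation date, "Date of discharge from ICU or date of death", and "Length of ITU stay". Below the list the protocol states: "The above data will be used to identify quantitative values for the primary and secondary endpoints discussed in section 13.1". Section 11.2 repeats the link for the case report form: "The data collected is listed in section 9".

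On timing, sections 6.2 and 8.1.1 admit patients from 1 April to 30 October 2020. The retrospective part in sections 7.1 and 9.1.1a covers 1 April to 1 June 2020. Section 11 plans "Retrospective data collection: 1st of July – 30th of October 2020". The Study Summary caps the patient datasets at 15.

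**The concern.** The label and the definition describe two different quantities. A 28-day proportion gives every patient the same time at risk and can be set beside other 28-day figures. A proportion dead by a calendar date mixes long and short follow-up and cannot be. Two analysts with the same charts could report different numbers, each with support in the same line of the protocol.

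The second problem is data capture. An endpoint can be reported only if its components are recorded, and the protocol names one list as the source for all of them. If that list is used as written, one endpoint lacks both of its dates, and the mortality endpoint may lack follow-up after ICU discharge. The gap is cheap to close before extraction. Afterwards, charts would have to be reopened.

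**Working it through.** The protocol gives no figure for these endpoints, so there is nothing to reproduce. The check is date arithmetic plus a comparison of the endpoint list with the data list.

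**1. Time at risk under the written definition.** Time at risk = end of period − admission date.

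- Period 1 April to 1 June (sections 7.1 and 9.1.1a): admission on 1 April gives 61 days and on 1 June gives 0. The last admission with a full 28 days is 1 June − 28 = 4 May. The last 28 of the 62 possible admission days give fewer than 28 days.
- Period 1 April to 30 October (sections 6.2 and 8.1.1): admission on 1 April gives 212 days and on 30 October gives 0. The last admission with a full 28 days is 2 October. The last 28 of 213 admission days give fewer.

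Neither period yields 28-day mortality. Two invented patients show errors in both directions, taking ICU admission as day 0:

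- Admitted 1 April, dies on day 40 (11 May). Counted under either period, but not a 28-day death.
- Admitted 20 May, dies on day 20 (9 June). A 28-day death, but not counted if the period ends on 1 June.

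With 15 patients, each such case moves the proportion by 1/15 = 6.7 percentage points.

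**2. Endpoint list against data list.**

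- Length of hospital stay needs the hospital admission and hospital discharge dates. Neither is in section 9.1.1a, which lists ICU admission, ICU discharge or death, and ITU stay.
- 28-day mortality needs a day 0 and vital status at day 28. Two candidates for day 0 are listed (ICU admission and intubation), but neither is chosen. Day-28 status is known for a patient who dies in ICU or is still there on day 28. For a patient who leaves ICU alive earlier, the either/or item is satisfied by the ICU discharge date, and no later status is listed.

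**3. Size of the gap in vital status.** With d known deaths by day 28, u patients of unknown status and n patients in all, mortality lies between d/n and (d + u)/n. The width is u/n. At n = 15, with u assumed because the protocol gives no count:

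| u | width (percentage points) |
|---|---|
| 1 | 6.7 |
| 3 | 20.0 |
| 5 | 33.3 |

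**4. Whether a fixed window is feasible.** The last retrospective admission is 1 June, and 1 June + 28 days = 29 June. Collection opens on 1 July, so day 28 from admission has passed for every retrospective patient before extraction starts. If day 0 is intubation, day 28 falls before collection closes on 30 October for anyone intubated by 2 October.

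**The case against.** The strongest reply is that little depends on this. Mortality is the last item in a long list of secondary, descriptive endpoints, in at most 15 patients, with no sample size calculation and no planned comparison. Section 13.2 also suggests that only adverse events may be reported if the anaesthetic-machine charts cannot be identified, which the protocol considers the likelier case. This stands as a limit on severity. It does not remove the point: section 9.1.1a says its remaining text is written for that likelier case, yet it still lists the clinical items and directs them to the section 13.1 endpoints.

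A second reply is that the data list is merely incomplete. The data collection forms are still to be designed, the hospital's electronic record already tracks patient locations, and the date of death is not expressly limited to deaths in ICU. This stands in part. If any later death were recorded, 28-day mortality could be derived. However, the item is worded as an alternative to ICU discharge, and the records named for review are observation charts and the daily sheets of ICU clinicians and physiotherapists. The electronic record is named only for generating the patient list. The conflict between label and definition and the missing hospital dates remain on any reading.

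A reader might infer three stronger points that the protocol does not support:

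- **That late admissions cannot reach day 28 before collection closes.** This would apply only to patients after 1 June, whose collection depends on a second surge and a protocol amendment (sections 9.1.1a and 9.1.1b).
- **That ward deaths will certainly be missed or that hospital dates are unobtainable.** The protocol shows only that it does not list them for collection.
- **That pooling deaths with survivors distorts the stay summaries.** How deaths are handled there is analysis detail that a statistical analysis plan may settle, and the protocol gives no figures from which to size an effect.

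**Conclusion.** The point holds. As written, the mortality rule does not produce the quantity it names, because time at risk ranges from 0 to 61 days, or from 0 to 212 days under the longer window, and no day 0 is set. Length of hospital stay cannot be calculated from the listed items. Day-28 status can be unknown for patients who leave ICU alive before day 28, at 6.7 percentage points of possible range per patient.

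The 6.7 points assume the maximum of 15 patients; with fewer, each patient counts for more. The vital-status part also assumes that the either/or item is completed as worded. A statistical analysis plan could tidy the definition, but it could not analyse dates that were never recorded.

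This is a should-fix matter. It affects the meaning and capture of secondary descriptive endpoints, and has no bearing on the primary endpoints, power or error rates.

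**What to change.** - In section 13.1.2, define the endpoint as death from any cause within 28 days of one stated day 0. ICU admission and intubation are both already recorded, so either can serve, provided one is named.
- In the section 9.1.1a list, add the hospital admission date, the hospital discharge date, and vital status with date of death irrespective of ICU discharge.
- Leave the retrospective collection dates as they are. If the prospective part is added by amendment, set its cut-off at least 28 days after the last patient's day 0. For a day 0 of 30 October that is 27 November, which is after the present close of collection on 30 October but before the scheduled study end on 30 November.

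The cost for the retrospective cohort is one reworded line and a few fields for at most 15 patients. The protocol's own electronic record is a plausible source for them, although it does not say that the record holds these dates. The prospective part would also need a longer collection period, which its amendment can set. The change should be made before extraction begins.

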13.2 STATISTICAL ANALYSIS PLANS

The retrospective (and prospective, if available) data collection:

This is a cohort study with no sample size calculation. The number of patients managed on AnMach and charts available (identified as AnMach Use) will dictate how many cases we will be able to analyse. The statistical analysis will be descriptive and performed with the Microsoft Office Excel data analysis package in case we will not be able to identify the AnMach charts and we will collect only adverse events data and report them as proportions. The clinical outcomes will be described using absolute and relative frequencies (expressed as a percentage) or position indices (average or median) and relative dispersion indices (standard deviation or interquartile range) suitable for the type of variable analysed. If comparison between AnMach patients and ITU ventilator patients will be possible, mean and standard

23

deviation of clinical outcomes for the two groups will be compared (the plan for this analysis will be explained in case of requesting a protocol amendment).

The Survey:

The questionnaire answers will be inserted in an excel spreadsheet and cleaned. Incomplete, inaccurate and missing data will be detected and discussed during interviews. The results will be used to select participants for the second stage and implement the topic guide for interviewing the volunteers. For this aspect of the study the statistical analysis will be descriptive and performed with the Microsoft Office Excel data analysis package. Data will be reported as proportions.

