5.2 RATIONALE

In order to meet the increased demand for ITU beds, in many hospitals in the UK, and in particular at the RFH, general care wards were transformed into ITUs in preparation for the surge. The ward 2North A (2NA) and the main recovery room at the RFH has been equipped with AnMach with a view to admit COVID-19 surge ventilated patients. Patients were looked after by either anaesthetic or intensive care consultants as well as ITU and non-ITU nurses and doctors.

Evidence around the use of AnMach for long-term ventilation and weaning of critically ill patients is scarce. Published studies are dated and based on test lung model and compare the performance of the AnMach and ICU ventilators in the laboratory settings (Jaber et al., 2006; Tung et al., 2005). Despite recently disseminated guidelines, professionals who managed surge patients admitted to 2NA/main recovery may have not been familiar with the equipment and not been aware of the newly published evidence.

This study aims to explore the clinical outcome of patients admitted to 2NA/main recovery in April and May 2020, identify possible adverse events related to the use of AnMach as ventilators, and capture the experience of staff using unfamiliar equipment and managing non typical cases. The results of our study will potentially allow us to identify additional risks of using AnMach as ITU ventilators rather than the ones published in the guidelines and to recognise hidden areas for improvement of care and staff support to address.

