9 STUDY PROCEDURES

9.1 PHASE 1 PROCEDURES: quantitative cohort study

9.1.1a - Retrospective data collection

The quantitative phase of this study aims to broadly examine the impact of using anaesthetic machines for ventilation of COVID-19 positive patients.

Important note: current inability to access the patient notes and observation charts (access to notes is requiring a quarantine period once a patient has been discharged from ITU; this is currently 2 weeks) may lead to partial availability of the data described in the endpoints section. Anecdotal evidence from discussions with nursing staff suggests that it may not be possible to tell from the documentation which patients were ventilated with AnMach versus a conventional ITU ventilator. This issue can only be addressed following accessing some of the observation charts that have been processed and released from quarantine. At this moment we can hypothesise two options:

Option I, we can label the charts as AnMach use: It will be possible to perform a clinical outcomes and adverse events comparison between patients identified as being ventilated by AnMach and those

identified as being ventilated by conventional ICU ventilators. In this case (less likely) we will request a study amendment after having access to the chart and being sure we can achieve this. We will also request an amendment in case of a second surge of COVID19 for the prospective data collection.

Option II, we cannot distinguish which device was used to ventilate the patients: adverse events possibly linked to AnMach will be recorded from charts of all patients admitted to 2NA and main recovery between the 1st April and the 1st of June 2020. We will also review Datix database for any serious incidents related to the use of AnMach.

The remaining sections refer to this option II = we cannot label charts as AnMach (more likely to be the case).

The Methods for Phase 1 of this study can be broken down into the following sections:

1. Identification of study participants:

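### The protocol gives conflicting rules on whether clinical-outcome data are collected under Option II, the scenario it expects

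*Protocol*

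**What the plan says.** Section 9.1.1a sets out two options and fixes the base case: "The remaining sections refer to this option II = we cannot label charts as AnMach". It calls this the more likely one. Four places then bear on what is collected in that case.

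- **Definition of Option II (9.1.1a).** "adverse events possibly linked to AnMach will be recorded from charts of all patients admitted to 2NA and main recovery", together with a review of the Datix incident database. No clinical outcome is named.
- **Data-recording list (9.1.1a, item 3).** "The data for each patient will be recorded and anonymised in an encrypted Excel spread sheet and will include" age and gender, APACHE II, SOFA, ventilation and weaning days, transfer, tracheostomy, adverse events, organ support, ITU stay and "Date of discharge from ICU or date of death". The list closes: "The above data will be used to identify quantitative values for the primary and secondary endpoints discussed in section 13.1".
- **Data collection tool (11.2).** For Phase 1 it refers the reader to section 9 for the data collected.
- **Statistical analysis plans (13.2).** If the anaesthetic-machine charts cannot be identified, "we will collect only adverse events data and report them as proportions". The next sentence, with no scenario attached, says how clinical outcomes will be summarised (frequencies, mean or median, SD or IQR).

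Section 13.2.2 adds that the Phase 1 analysis is descriptive in this scenario and does not limit it to adverse events. The rationale (5.2) states the purpose: "This study aims to explore the clinical outcome of patients admitted to 2NA/main recovery in April and May 2020".

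**The concern.** For one scenario the protocol gives two collection rules. One produces a severity-adjusted picture of a small cohort in the descriptive sense: who the patients were, how ill they were, how long they were ventilated and whether they survived. The other produces a single adverse-event proportion with no age, APACHE II or SOFA beside it to show how ill those patients were.

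The restricting clause limits what is collected, not just what is reported, so a later analysis plan could not repair it: data never abstracted cannot be analysed. If it were followed, the aim in 5.2 of exploring clinical outcome could not be met. If the matter is left open, the choice could be made after the charts have been seen.

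**Working it through.** The protocol has no sample size calculation and no stated figure to reproduce. The check is a comparison of sections and a count of endpoints.

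**1. Is it the same scenario?** Yes. Option II in 9.1.1a is the case where charts cannot be labelled by device, and the condition attached to the restricting clause in 13.2 is that the anaesthetic-machine charts cannot be identified.

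**2. Which texts point which way?**

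- Adverse events only: the Option II definition in 9.1.1a and the restricting clause in 13.2.
- Broad dataset: the item 3 list in 9.1.1a and the pointer in 11.2.
- Consistent with the broad dataset but silent on collection: the sentence on clinical outcomes in 13.2, and 13.2.2.

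Both 9.1.1a and 13.2 are therefore internally inconsistent. The conflict is not simply one section against the other.

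**3. Endpoints at stake.** Section 13.1.1 has 2 primary endpoints (adverse-event proportion, weaning failure). Section 13.1.2 has 15 secondary bullets. Total: 2 + 15 = 17.

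**4. Under the restricting clause, read literally.** The adverse-event proportion keeps its data. No secondary bullet is adverse-event data. Endpoints without data: 17 − 1 = 16, that is, weaning failure plus all 15 secondary bullets.

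**5. How many of the 16 depend on the device label?** Weaning failure, because it is defined while on the anaesthetic machine, and three secondary bullets: number ventilated on an anaesthetic machine, days to transfer, and indication for transfer. That is 1 + 3 = 4. These are compromised by Option II whatever 13.2 says. Device-independent: 16 − 4 = 12.

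**6. Does the 9.1.1a list supply those 12?** Not entirely.

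- Length of hospital stay has no source item: the list has no hospital admission or discharge date.
- 28-day mortality is only partly covered: an item giving ICU discharge or death does not clearly capture deaths after ICU discharge.
- The other 12 − 2 = 10 have a listed item or can be built from listed items.

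**7. Is the restriction needed?** No. Option II defines the cohort by location (ward 2NA and main recovery), and the 12 device-independent bullets can be described for that cohort without a device label. For the other four, 9.1.1a itself expects nursing charts and physiotherapy notes to identify the device for individual patients, so reporting on a documented subset may be possible.

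**The case against.** A reader might infer that following 13.2 simply leaves every clinical endpoint, mortality included, without data. The documents do not support that as a flat statement.

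- The sentence after the restricting clause plans to describe clinical outcomes and carries no condition. The device comparison comes later, under its own condition.
- Section 11.2 points to section 9 for the data collected, which favours the broad list.
- Section 13.2.2 keeps a descriptive primary and secondary endpoint analysis in this scenario.

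On this view there is one stray clause among neighbours that contradict it. That limits the claim: total loss follows only if the clause governs. It does not remove the conflict. If the sentence on clinical outcomes applies under Option II, 13.2 contradicts itself in consecutive sentences, since outcomes not collected cannot be described. If it applies only when the device can be identified, the loss is real. Section 13.2.2 says the analysis is descriptive, not what is collected. And the restriction is not isolated, because the Option II definition in 9.1.1a has the same narrow scope.

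A reader might also blame the clause for all 16 endpoints. That is too much: four are compromised by Option II itself, and the broad list would not fully supply two more.

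It is also fair to say that the consequences are bounded. The study is descriptive, plans no powered comparison and caps patient datasets at 15.

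**Conclusion.** The point holds as an internal contradiction: the protocol does not say consistently whether clinical-outcome data are collected in the scenario it considers more likely. In the worst case, with the restricting clause in force, 16 of 17 Phase 1 endpoints have no data. Of these, 4 are compromised under Option II regardless. Among the other 12, 10 would be supplied by the 9.1.1a list as it stands, 28-day mortality in part, and length of hospital stay not at all.

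This rests on three assumptions: that Option II is the case that arises; that each secondary bullet counts as one endpoint; and that the mortality endpoint is meant at 28 days, as its label says. The protocol should be corrected, but this is a matter of reconciling text and not a proven loss of the study's outcomes.

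**What to change.** - **13.2:** delete the clause that restricts collection to adverse events. **9.1.1a:** amend the Option II definition to match. Both should state that the full 9.1.1a list is collected under Option II.
- **Denominators:** report device-independent items descriptively for patients admitted to 2NA/main recovery from 1 April to 1 June 2020. Report device-dependent items (weaning failure, number on an anaesthetic machine, days to transfer and indication for transfer) only for patients whose charts document the device, and give that number.
- **Adverse-event primary endpoint:** state which of these two denominators it uses. Some of its components, such as soda lime issues, are specific to the device.
- **9.1.1a list:** add hospital admission and discharge dates and vital status at 28 days.
- **Eligibility:** reconcile the location-defined cohort with the Phase 1 criteria. Section 8.1.1 requires ventilation on an anaesthetic machine, 8.1.2 excludes patients on an ITU-grade ventilator from admission, 8.1 allows no exceptions, and step 1 of 9.1.1a applies the inclusion criteria to the location list.

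The cost is protocol wording, a few added dates and a little more abstraction from charts already being opened for adverse events. It is small because section 3.0 caps patient datasets at 15. If the location cohort proves larger than that, the cap needs to be reconciled as well.
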